This will be a 24 week, randomized, double-blind, prospective multi-center trial evaluating the ability of salmeterol to permit a stepwise reduction in inhaled corticosteroids in patients with moderate asthma. All patients with moderate asthma who meet the inclusion and exclusion criteria will receive both a methacholine bronchoprovocation (if baseline FEV₁ ≥ 55% predicted) followed by a sputum induction with hypertonic saline (if post-albuterol FEV₁ > 60% predicted). They will then be treated for a six week run-in period with a uniform dose of ICS (triamcinolone acetonide 400 µg BID) and prn use of the intermediate acting β₂-agonist, albuterol. Beginning with the run-in period, subjects will record in a daily diary their daytime and nighttime symptoms (dyspnea, wheeze, cough, each scored 0-3), AM and PM PEFs, albuterol use, and intercurrent illnesses and hospitalizations. At the end of the run-in period, patients will be randomized within either the SOCS or SLIC protocol based on FEV₁ measurements at the week six visit, and the stability of their PEF measurements during the preceding two weeks. (See diagram, page 24) Patients with greater airflow limitation (FEV₁ ≤ 80% predicted), or greater pulmonary function instability (variability > 20% but FEV₁ > 80% predicted), will be selected for the SLIC protocol. At the end of the six-week run-in period, patients will be randomized in a 2:13 ratio to placebo BID (Group A) and salmeterol 42 µg BID (Group B/C), respectively, for a period of two weeks. At the end of week eight, patients in Group B/C will be classified into subgroup I (FEV₁ > 80% and PEF variability over previous two weeks ≤ 20%) and subgroup II [FEV₁ ≤ 80% predicted or (FEV₁ > 80% predicted and PEF variability over previous two weeks > 20%)]. Then a stratified randomization will take place within each subgroup such that patients in Group B/C will be randomized to Group C (a two step dose reduction/elimination in ICS if they meet safety criteria) (800 – 400 µg at week 8, and 400 – 0 µg at week 16), and Group B (a sham stepwise reduction). All patients in Group A will also undergo a two step dose reduction identical to Group C. After qualifying for SLIC, all patients will receive 2 puffs of salmeterol (42µg) (single blind); one hour later, if their FEV₁ ≥ 55% predicted, methacholine bronchoprovocation will be performed. They will visit the clinical center every 2-4 weeks for an interval history and physical examination, diary review, quality of life measurements, and spirometry (see detailed schematic). At all subsequent visits patients in Groups A, B and C will receive 2 puffs of salmeterol (single blind) and, at designated visits, this will be followed one hour later by methacholine bronchoprovocation if their baseline FEV₁ ≥ 55% predicted. Sputum induction for analysis of markers of inflammation will not be performed at any subsequent visit. Patients will be assigned treatment failure status if their pulmonary function, beta agonist use, or symptom control significantly worsens as defined by a set of strict criteria. If this occurs prior to the scheduled end of the study, the patients may be rescued using a steroid burst algorithm, while at the same time increasing their dose of triamcinolone acetonide to the baseline dose of 800 µg/day. The patients will continue to be followed and all scheduled visits and testing will occur but no further inhaled corticosteroid dose reductions will be attempted. Patients will continue to take their study salmeterol (or placebo) unless the physician can document that treatment failure status was causally related to taking this medication. Glaxo, Inc. has kindly agreed to supply active and placebo canisters for albuterol (Ventolin[®]) and salmeterol xinafoate (Serevent[®]), and Rhône-Poulenc Rorer has graciously consented to supply active and placebo canisters for triamcinolone acetonide (Azmacort[®]) to be used in this protocol.

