If the prebronchodilator FEV₁ value at Visit 5 or later is $\leq 80\%$ of the PREbronchodilator value obtained at Visit 4, the patient should be given albuterol (≥ 6 puffs in one hour) to assess the degree of reversibility in his/her airflow obstruction. These values must be reported to the physician responsible for the care of the ACRN patient on that day. If the physician determines that the subject's response to the bronchodilator is satisfactory, and the patient's clinical condition is stable, the patient may continue in the study, provided he/she returns to the ACRN study site in 24-96 hours for repeat spirometry. In addition, the clinic coordinator or designee shall telephone the patient every 24 hrs to assess his/her condition. Prior to leaving the clinic, the patient should receive the usual doses of his/her study medications; no additional procedures scheduled for that study day shall be performed. At the additionally scheduled visit within the next 4 days, the repeat spirometric PREbronchodilator FEV₁ value must be $> 80\%$ of PREbronchodilator value obtained at Visit 4; if not, the patient will be considered a treatment failure at that time. If spirometric values are within the acceptable range, all procedures for the previously scheduled visit shall be performed according to the MOP and the patient will continue on his/her study medications.

Additional Treatment Failure Criteria:

1. Any use of oral or parenteral corticosteroids related to the treatment of the patient's asthma.
2. Occurrence of a significant exacerbation during the double-blind period.
3. Need for emergency treatment at a medical facility that is related to, or complicated by, the patient's asthma and which results in corticosteroid treatment or hospitalization for an acute asthma exacerbation.
4. Physician clinical judgment for safety reasons.

G. Criteria for Inhaled Corticosteroid Dose Reduction

1. The inhaled corticosteroid dose will be reduced from 800 to 400 μg at visit 5 and from 400 to 0 μg on visit 7, unless the patient has met the criteria for treatment failure status on the day of their visit or in the interval since their last visit.

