If patients meet criteria for treatment failure status, their dose of inhaled corticosteroids will be increased to the dose they were receiving at visit 4 (800 μ g/day) delivered by an open-label inhaler. Study inhalers of corticosteroids (or its placebo) will be returned to the clinical center. If they meet the criteria detailed in Section VI, they will be treated with appropriate rescue algorithms for an asthma exacerbation. Study inhalers of salmeterol (or placebo) will be continued unless the physician can document that treatment failure status was causally related to taking this medication. They will continue to participate in the study until its termination (intent-to-treat analysis), but no further reductions in inhaled corticosteroid dose will be attempted during this time period. For safety reasons, all subjects will be seen within one week (\pm 3d) from the day they were categorized as achieving treatment failure status. Following this "safety" visit, subsequent protocol visits will continue in accordance with the visit schedule established at Visit 1 (see SOCS/SLIC MOP for details concerning possible replacement of scheduled protocol visits with treatment failure related visits).

Drug Swap Visit, Week 10

Patients will return to the clinical center 2 weeks after Visit 5. The "salmeterol" inhaler will be exchanged during this visit. Diary cards will be reviewed to determine whether the patient is showing signs of treatment failure. Specifically, the coordinator will inquire about rescue β -agonist use, peak flow measurements and day and nocturnal symptoms. If it is

determined that the patient fulfills criteria for treatment failure, a treatment failure visit will be completed and study medications will be adjusted accordingly.

Visit 6, Week 12

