Patients will return to the clinical center at the same time of day as on week 0, \pm 2 hours. Quality of life questionnaires will be administered. Spirometry will be obtained. The patient's AirWatch will be tested against the Jones-Flow Volume calibrator and will be replaced if it does not meet defined quality control standards. Adverse events will be assessed and recorded using the protocol outlined by the ACRN. Diary cards will be reviewed and new ones dispensed; AirWatch data will be uploaded. Clinical center personnel will review the appropriateness of the timing of medication use, peak flow recording and symptom recording. All patients should have withheld their rescue inhaler for at least 6 hours and their salmeterol (or placebo) inhaler for at least 12 hours prior to the visit. Following baseline spirometry, all patients will receive 2 puffs of salmeterol (42 μ g) (single blind). One hour later, if the postbronchodilator FEV₁ \geq 55% predicted, methacholine bronchoprovocation will be performed. Guidelines for peak flow safety limits and rescue medication use will be reviewed. If the patient does not meet criteria for treatment failure, they will receive two new coded, double-blind "steroid" inhalers to be taken 2 puffs twice daily. They will also receive a new "salmeterol" inhaler (placebo in Group A, active drug in Groups B and C) inhaler and will be further instructed to maintain at a dose of 2 puffs twice daily. Following methacholine bronchoprovocation, 2 puffs of albuterol will be administered. Open label albuterol will be issued as needed. Patients will be instructed to return to the clinical center in 2 weeks.

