Patients will return to the clinical center at the same time of day as on week 0, \pm 2 hours. Following baseline spirometry, all patients will receive 2 puffs of salmeterol (42 μ g) (single blind). One hour later postbronchodilator spirometry will be obtained (i.e., salmeterol reversibility testing). The patient's AirWatch will be tested against the Jones-Flow Volume calibrator and will be replaced if it does not meet defined quality control standards. Adverse events will be assessed and recorded using the protocol outlined by the ACRN. Diary cards will be reviewed and new ones dispensed; AirWatch data will be uploaded. Clinical center personnel will review the appropriateness of the timing of the medication use, peak flow recording and symptom recording. If the patient does not meet criteria for treatment failure, they will receive two new coded, double-blind "steroid" inhalers to be taken 2 puffs twice daily. They will also receive a new "salmeterol" inhaler (placebo in Group A, active drug in Groups B and C) and will be further instructed to maintain a dose of 2 puffs twice daily. Open label albuterol will be issued as needed. Patients will be instructed to return to the clinical center in 2 weeks.

If patients meet criteria for treatment failure status, their dose of inhaled corticosteroids will be increased to the dose they were receiving at visit 4 (800 μ g/day) delivered by an open-label inhaler. Study inhalers of corticosteroids (or its placebo) will be returned to the clinical center. If they meet the criteria detailed in Section VI, they will be treated with appropriate rescue algorithms for an asthma exacerbation. Study inhalers of salmeterol (or placebo) will be continued unless the physician can document that treatment failure status was causally related to taking this medication. They will continue to participate in the study until its termination (intent-to-treat analysis), but no further reductions in inhaled corticosteroid dose will be attempted during this time period. For safety reasons, all subjects will be seen within one week (\pm 3d) from the day they were categorized as achieving treatment failure status. Following this "safety" visit, subsequent protocol visits will continue in accordance with the visit schedule established at Visit 1 (see SOCS/SLIC MOP for details concerning possible replacement of scheduled protocol visits with treatment failure related visits).

Telephone call, Week 19

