In the event of a "treatment failure" (see section III.F), patients will be instructed to come into the Clinical Center as soon as possible, preferably within 72 hours and ideally within 24 hours, in order to have their condition assessed. At this time, the patient will complete Quality of Life Questionnaires, undergo spirometry, and complete a physical exam with adverse events assessment. If the examining physician feels it is safe for the patient to continue, salmeterol reversibility testing will also be performed. Peak flow measures and rescue inhaler use will be reviewed on the diary cards. Any non-study drugs taken prior

to this visit will be documented. If patients meet criteria for treatment failure status, their dose of inhaled corticosteroids will be increased to the dose they were receiving at visit 4 (800 $\mu\text{g}/\text{day}$) delivered by an open-label inhaler. Study inhalers of corticosteroids (or its placebo) will be returned to the clinical center. Study inhalers of salmeterol (or placebo) will be continued unless the physician can document that treatment failure status was causally related to taking this medication.

If they meet the criteria detailed in Section VI, they will be treated with appropriate rescue algorithms for an asthma exacerbation. Trial salmeterol will be continued during exacerbations unless the treating physician considers it appropriate to suspend such therapy until the exacerbation resolves. Reinstitution of trial salmeterol will occur when the exacerbation has resolved at the discretion of the investigator. A record of all medications, dosages, and frequency of occurrence will be kept during exacerbations (see Section VI for additional information regarding the medical management of significant asthma exacerbations).

They will continue to participate in the study until its termination (intent-to-treat analysis), but no further reductions in inhaled corticosteroid dose will be attempted during this time period. For safety reasons, all subjects will be seen within one week ($\pm 3\text{d}$) from the day they were categorized as achieving treatment failure status. Following this "safety" visit, subsequent protocol visits will continue in accordance with the visit schedule established at Visit 1 (see SOCS/SLIC MOP for details concerning possible replacement of scheduled protocol visits with treatment failure related visits).

F. Protocol In Tabular Form

ICS = Inhaled corticosteroid MDI; AS = Active salmeterol MDI;

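### Clinic salmeterol is ordered for every patient at Visits 5 to 11, with no exemption for a retained patient whose trial salmeterol was stopped as the documented cause of treatment failure

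*Protocol*

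**What the plan says.** Two sets of instructions in the protocol apply to the same patient.

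**Stopping trial salmeterol.** After treatment failure, the blinded salmeterol or placebo inhaler is continued "unless the physician can document that treatment failure status was causally related to taking this medication". The rule stands in III.G.2, in the treatment-failure paragraphs of V.E for Visits 5 to 10, and at the Treatment Failure Visit; II.D has the same rule. The patient is not withdrawn. II.D says of treatment failures: "The patients will continue to be followed and all scheduled visits and testing will occur".

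**Giving salmeterol in clinic.** For the visits after Visit 4, II.D says: "At all subsequent visits patients in Groups A, B and C will receive 2 puffs of salmeterol (single blind". V.E repeats this visit by visit: "Following baseline spirometry, all patients will receive 2 puffs of salmeterol". At Visits 5, 6, 7, 9 and 11 a methacholine challenge follows, subject to FEV1 of at least 55% predicted. At Visits 8 and 10 there is spirometry only: "One hour later postbronchodilator spirometry will be obtained (i.e., salmeterol reversibility testing". The table in V.F agrees on which visits carry a challenge.

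A physician's safety judgement on the clinic salmeterol test is written in one place, the Treatment Failure Visit: "If the examining physician feels it is safe for the patient to continue, salmeterol reversibility testing will also be performed".

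**The concern.** The protocol foresees a patient in whom salmeterol is documented as the cause of treatment failure. It takes the inhaler away, keeps the patient in follow-up, and then orders the same drug in clinic at every remaining visit, with a bronchoconstrictor challenge after it at some of them. A coordinator following the visit text would re-expose the patient. A physician who withheld the dose would be departing from the written procedure.

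What is at stake is participant safety and clear instruction to sites. The primary analysis is not at risk. X.E counts treatment failures after Visit 5, so for a failure in that window the re-exposure follows the event, and a failure before Visit 5 lies outside the window.

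**Working it through.** The protocol has no figure of its own to reproduce here. The check is a reading of the text, a count of visits, and a rough bound on the number of patients.

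**1. Does any provision exempt this patient?**

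- *FEV1 of at least 55% predicted (V.E).* At the scheduled visits this is read one hour after the salmeterol dose, so it can stop only the methacholine.
- *Addendum to III.F.* If prebronchodilator FEV1 is at or below 80% of the Visit 4 value, "no additional procedures scheduled for that study day shall be performed". This depends on lung function, not on why the inhaler was stopped, and it is lifted on recovery: "If spirometric values are within the acceptable range, all procedures for the previously scheduled visit shall be performed according to the MOP".
- *Physician judgement.* Written for the Treatment Failure Visit and not carried to Visits 5 to 11.
- *Suspension during exacerbations (VI.A, VI.C).* Concerns the trial inhaler, not the clinic dose.
- *Removal from the study (VII.B.1, VII.B.2).* Provided for exacerbations that are too frequent or severe, or for cardiac abnormality. It ends participation and is not a test exemption for a patient who stays.

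Exemptions found: none. A patient whose FEV1 has recovered passes both FEV1 gates.

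**2. How much re-exposure is scheduled?**

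Clinic doses fall at Visits 5, 6, 7, 8, 9, 10 and 11 (7 visits) and challenges at Visits 5, 6, 7, 9 and 11 (5 visits).

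| Trial salmeterol stopped | Clinic doses left | Challenges left |
|---|---|---|
| Before Visit 5 | 7 | 5 |
| Between Visits 5 and 6 | 6 | 4 |
| Between Visits 6 and 7 | 5 | 3 |
| Between Visits 7 and 8 | 4 | 2 |
| Between Visits 8 and 9 | 3 | 2 |
| Between Visits 9 and 10 | 2 | 1 |
| After Visit 10 | 1 | 1 |

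For failures in the primary window the maximum is 6 doses and 4 challenges.

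**3. How many patients?**

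Inputs from X.F: failure rates of 60% (A), 5% (B) and 20% (C), with 20, 65 and 65 patients.

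- Expected failures: A 0.60 × 20 = 12; B 0.05 × 65 = 3.25; C 0.20 × 65 = 13. Total 28.25, of which B and C give 16.25.
- The share of failures attributed to salmeterol is not given. **Assumption:** 0 to 10%.
- B and C: 0 to 0.10 × 16.25 = 1.625 patients, at most 1.625/130 = 1.25%.
- A: 0 to 0.10 × 12 = 1.2 patients. Their stopped inhaler was placebo, but under masking they are handled alike and would still get active drug in clinic.
- All groups: 0 to 2.825 patients, at most 2.825/150 = 1.9%.

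The only bound that needs no assumed share is the total of about 28 expected failures. The true number is probably far below that and may be zero, because a masked physician has to document causation.

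**The case against.** The strongest reply is that the two rules govern different things: one a twice-daily inhaler, the other a single supervised test dose. Nothing in the protocol shows that a failure attributed to regular use makes one such dose unsafe. Continued testing after failure also looks deliberate. Section V.G chose the one-hour interval to bring out any adverse effect of chronic salmeterol on bronchoprotection, and a patient thought harmed by the drug is informative for that question. The protocol further refers methacholine procedure, drug-related effects and the replacement of visits after failure to manuals of operations, and VI.A says that exacerbations affect how later visits and diagnostic studies are arranged.

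Part of this stands. The exposure is limited, the number affected is unknown, and an exemption would remove post-salmeterol values selectively in the patients thought harmed. The rest does not close the gap. The passage in VI.A is a general introduction and waives no test. The manuals are not at hand, so what they say on this case is unknown, and they cannot be presumed to override an explicit protocol instruction. Continued testing may well be intended for treatment failures in general, but nothing shows that it was considered for the patient taken off the drug for cause. The authors did attach a safety judgement to the same test at the Treatment Failure Visit.

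**Conclusion.** The concern holds, as a minor one. Followed as written, the protocol re-doses a retained patient with the drug documented as the cause of treatment failure, up to six times for a failure in the primary window, with up to four methacholine challenges. Under an assumed attribution share of 0 to 10% and the protocol's planned failure rates, 0 to about 3 of 150 patients would be affected. That count rests entirely on the assumed share; the reading of the text does not. Sample size, power and the primary comparison are unaffected. A manual of operations may already cover the case, which cannot be verified from the protocol.

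**What to change.** Add one sentence to II.D and refer to it at Visits 5 to 11:

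*When a patient's trial salmeterol (or placebo) has been stopped as the documented cause of treatment failure, the clinic salmeterol dose and the methacholine challenge after it are omitted at all later scheduled visits; every other visit procedure continues.*

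The rule turns on the inhaler having been stopped, not on the treatment arm, so masking is kept. All other treatment failures are tested as planned.

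The cost is one sentence and seven references. Post-salmeterol FEV1 and PC20, which feed the bronchoprotection outcome in IV, would be missing for the exempted patients only. Under the assumed share, between 28.25 − 2.825 = 25.4 and 28.25 of the expected failures would still be tested. Because the missing values are related to outcome, the reason for omission should be recorded. No primary outcome data are lost.
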